### 7.1.1.1. Decline in Pulmonary Function

For participants not on augmentation therapy, the occurrence of the events detailed as A and B below will result in temporary discontinuation of study intervention in the affected participant. These events will necessitate review and adjudication by the DSMC. If, in the opinion of the DSMC, the decline in pulmonary function (as defined by events A or B, below) is likely related to something other than the study drug, e.g., a common cold, dosing in that participant may continue, otherwise, dosing of the participant can be permanently discontinued at the discretion of the Investigator.

- A. **FEV1:** At least 2 pulmonary function tests showing relative decrease from baseline of  $\geq 15\% \text{ AND}$  an absolute decrease from baseline of > 200 mL in FEV1 following administration of bronchodilators over a period of at least 3 months.
- B. DLCO: At least 2 pulmonary function tests showing a relative decrease from baseline of ≥ 15% in Hb-corrected DLCO AND an absolute decrease from baseline of > 6.5 mL/min/mmHg in Hb-corrected DLCO, following administration of bronchodilators over a period of at least 3 months.

### 7.1.1.2. Drug-Induced Liver Injury Monitoring

### For Participants with Normal Liver Biochemistries at Baseline

Study intervention will be discontinued when a participant meets one of the conditions outlined below (from Guidance for Industry-Drug Induced Liver Injury: Premarketing Clinical Evaluation [FDA, 2009]) or if the Investigator believes that it is in the best interest of the participant. Safety laboratories will be monitored by a central laboratory in real time with potential drug-induced liver injury (DILI) alerts sent to the Investigator.

- $\circ \quad \text{ALT or AST} > 8 \times \text{ULN}$
- ALT or AST >  $5 \times$  ULN for more than 2 weeks
- ALT or AST  $> 3 \times$  ULN and (total bilirubin  $> 2 \times$  ULN or INR > 1.5)
- $\circ$  ALT or AST > 3 × ULN with the appearance of fatigue, nausea, vomiting, right upper quadrant pain or tenderness, fever, rash, and/or eosinophilia (> 5%)

Participants should be monitored at each study visit and instructed to call the Investigator for new or worsening symptoms of clinical hepatitis. Both symptoms and calls should be documented in source notes.

NOTE: Any elevation in an LFT leading to discontinuation of study intervention must be at least possibly related to the investigational drug, and other potential causes (e.g., strenuous exercise, use of concomitant medication) must have been excluded.

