### 7.1.1. Stopping Rules for Individual Participants

Discontinuation of treatment can be decided by either the Investigator or the participant. Participants who discontinue trial product should continue with the scheduled visits and assessments. If the participant does not wish to attend the scheduled clinic visits, efforts should be made to have visits converted to phone contacts. However, all efforts should be made to have the participant attend the visits at week 24, 48 and 96, as applicable.

The trial product must be discontinued, if any of the following applies for the participant:

1. Decline in Pulmonary Function (see Section 7.1.1.1)

2. Abnormal liver blood parameters indicating DILI (see Section 7.1.1.2)

3. Pregnancy/ Intention of becoming pregnant

4. Simultaneous use of an approved or non-approved investigational medicinal product in another clinical trial

5. Safety concerns as judged by the Investigator

Participants meeting any of the above treatment discontinuation criteria are allowed to resume trial product, if the criterion is no longer met.

For Germany: please also see country-specific requirements in Section 10.5.

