### Assessments in Case of Increased Levels of Liver Blood Parameters

For all such events listed above repeated testing must occur within 48 to 72 hours and work up for competing etiologies must be performed including:

- Complete liver profile including ALT, AST, alkaline phosphatase, conjugated bilirubin, total bilirubin and INR. Hereafter repeat testing should be done 2 to 3 times weekly. If close monitoring is not possible the trial product should be discontinued. The frequency of repeat testing can decrease to once a week or less if abnormalities stabilize and the participant is asymptomatic.
- A detailed history of symptoms and prior or concurrent diseases.
- History of concomitant drug use (including non-prescription medications and herbal and dietary supplement preparations), alcohol use, recreational drug use, and special diets.
- Ruling out acute viral hepatitis (including hepatitis A, B, C and E); autoimmune or alcoholic hepatitis; hypoxic/ischemic hepatopathy; and biliary tract disease.
- Obtaining a history of exposure to environmental chemical agents.

Trial product can be restarted if an alternative etiology is definitively identified, and liver blood parameters have returned to pre-event levels.

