#### Assessment of Causality

The Investigator is obligated to assess the relationship between study intervention and each occurrence of each AE/SAE. A "reasonable possibility" of a relationship conveys that there are facts, evidence, and/or arguments to suggest a causal relationship, rather than a relationship cannot be ruled out.

The Investigator will use clinical judgment to determine the relationship. Alternative causes, such as underlying disease(s), concomitant therapy, and other risk factors, as well as the temporal relationship of the event to study intervention administration, will be considered and investigated. The Investigator will also consult the Investigator's Brochure and/or Product Information for marketed products in his/her assessment.

For each AE/SAE, the site personnel **must** document in the medical notes that he/she has reviewed the AE/SAE and has provided an assessment of causality.

There may be situations in which an SAE has occurred, and the Investigator has minimal information to include in the initial report. However, it is very important that the Investigator always make an assessment of causality for every event before the initial transmission of the SAE data to the SAE Coordinator. The Investigator may change his/her opinion of causality in light of follow-up information and send a SAE follow-up report with the updated causality assessment.

The causality assessment is one of the criteria used when determining regulatory reporting requirements. The following definitions will be used in assessing causality:

- Not Related: Event for which sufficient evidence exists to conclude that the etiology is unrelated to study intervention.
- **Possibly Related**: There is some temporal relationship between the event and the administration of the study intervention, and the event is unlikely to be explained by the participant's medical condition or other therapies.
- **Probably Related**: The temporal relationship between the event and administration of the study intervention is suggestive, and the event is unlikely explained by the participants' medical condition or other therapies.
- **Definitely Related**: The event follows reasonable temporal sequence from the administration of the study intervention, follows a known or suspected response pattern to the study intervention, is confirmed by improvement upon stopping the study intervention, and reappears upon repeated exposure if that occurs.

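### For participants with normal baseline liver tests, a NOTE that other causes must already be excluded contradicts the mandatory stop at a liver-injury threshold

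*Protocol*

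**What the plan says.** Section 7.1.1 of the protocol sets the parent rule: "The trial product must be discontinued, if any of the following applies for the participant". Item 2 on its list is liver blood parameters indicating DILI, with a reference to Section 7.1.1.2. Item 5 is "Safety concerns as judged by the Investigator". The section adds that participants who meet a criterion "are allowed to resume trial product, if the criterion is no longer met".

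For participants with normal liver biochemistry at baseline, Section 7.1.1.2 begins: "Study intervention will be discontinued when a participant meets one of the conditions outlined below". Four conditions follow:

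- ALT or AST above 8 x ULN
- ALT or AST above 5 x ULN for more than 2 weeks
- ALT or AST above 3 x ULN with total bilirubin above 2 x ULN or INR above 1.5
- ALT or AST above 3 x ULN with symptoms or eosinophilia

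The investigator may also stop drug in the participant's best interest. A NOTE then says that any liver-test elevation leading to discontinuation must be "at least possibly related to the investigational drug, and other potential causes (e.g., strenuous exercise, use of concomitant medication) must have been excluded".

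The assessments subsection that follows says: "For all such events listed above repeated testing must occur within 48 to 72 hours and work up for competing etiologies must be performed". Its restart rule is: "Trial product can be restarted if an alternative etiology is definitively identified, and liver blood parameters have returned to pre-event levels".

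**The concern.** Excluding other causes is the result of a work-up, and the protocol starts that work-up only once the threshold has been crossed. Read literally, the NOTE makes a finished work-up a precondition for the stop. A rule worded as mandatory then becomes a site-by-site judgement exactly while the cause is unknown.

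The restart rule puts the burden the other way: drug is off, and comes back once another cause is definitively shown. The NOTE asks for other causes to be ruled out before drug comes off.

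Raised liver tests are a named key risk in Section 2.3.4, although that section also reports no clinically significant or dose-dependent rise in AST or ALT after single doses in healthy volunteers. The third condition uses the same cut-offs by which Section 5.2 defines hepatotoxicity for prior oligonucleotide therapy, so the NOTE qualifies the stop for a pattern the protocol itself treats as serious.

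**Working it through.** The plan has no figure to reproduce here. The check compares the rules, works examples through them, and asks when a dose could be affected.

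**Order of stop and causality judgement**

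| Rule | Causality judged before the stop? |
|---|---|
| Section 7.1.1, item 2 | No |
| 7.1.1.2, normal baseline, opening sentence | No |
| 7.1.1.2, normal baseline, NOTE | Yes, other causes already excluded |
| 7.1.1.2, elevated baseline algorithm | No |
| 7.1.1.1, lung function | No: dosing is held, then the DSMC judges cause |
| 7.1.1.2, restart rule | Cause considered at restart |

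The NOTE is the only outlier.

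**Worked cases**

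- *A.* Baseline ALT 1 x ULN, on study 9 x ULN, a new medicine not yet excluded. Opening sentence: 9 > 8, stop. NOTE: condition not met, so the stop rests on discretion.
- *B.* ALT 3.5 x ULN with bilirubin 2.5 x ULN and the same open cause. Opening sentence: 3.5 > 3 and 2.5 > 2, stop. NOTE: not met.
- *Contrast.* Screening ALT 1.5 x ULN. The elevated-baseline rule stops drug above 5 x 1.5 = 7.5 x ULN with no causality condition.
- *C (resuming).* ALT falls from 9 to 2 x ULN, with no symptoms, normal bilirubin and INR, and the cause unresolved. The resume sentence in Section 7.1.1 allows dosing, because no criterion is still met. The liver restart rule does not: no other cause has been identified, and 2 is above the pre-event 1.

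**People**

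Cohorts 1 and 2 have up to 8 + 8 = 16 participants randomized 3:1, so 16 x 3/4 = 12 on active drug. The number with normal baseline tests is not given. Cohort 3 never enrolled (SAP Sections 1 and 5.2).

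**When a dose could be affected**

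A dose is at issue only if it falls due while the work-up is open and discretion is not used. Gaps from a scheduled safety sample to the next dose in Cohorts 1 and 2, from the Schedules of Activities:

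| Sample to dose | Nominal | Shortest | Longest |
|---|---|---|---|
| Day 15 (±2) to Day 29 (±2) | 14 days | 27 − 17 = 10 | 31 − 13 = 18 |
| Day 57 (±5) to Day 85 (±5) | 28 days | 80 − 62 = 18 | 90 − 52 = 38 |
| Day 421 (±7) to Day 505 (±7) | 84 days | 498 − 428 = 70 | 512 − 414 = 98 |

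Even in 10 days the required retesting gives 1 panel by 72 hours plus 2 to 3 in the remaining 7 days, so 3 to 4 panels.

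The gap can be shorter when a threshold is crossed on a repeat test. The condition of more than 2 weeks above 5 x ULN, counted from Day 57, is met at Day 57 + 15 = 72 at the earliest, 85 − 72 = 13 days before the next dose. At the window limits it is met at Day 62 + 15 = 77, only 80 − 77 = 3 days before a Day 80 dose.

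**The case against.** The strongest reply is that the rest of the section is not purely stop-first. The assessments subsection also says drug should be discontinued if close monitoring is not possible, which has little purpose if drug is always off already. The parent rule speaks of parameters indicating DILI, so drug causation is arguably built in and the NOTE is loose clarification. The close-monitoring sentence does add ambiguity, but it fits the close-monitoring tier of the elevated-baseline algorithm, which runs with or without drug, and it is conditional. The parent rule points to criteria that are laboratory values and symptoms, not a causality judgement.

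A second reply is that safeguards are layered: item 5 in Section 7.1.1, the best-interest clause, real-time central-laboratory alerts, discussion with the Medical Monitor (Section 8), and DSMC adjudication of potential stopping rules (Section 9.4.1). No sentence orders dosing to continue. All of this is true and lowers the risk. Item 5 is itself a mandatory stop, but only once the investigator judges there is a safety concern; the others permit or prompt a stop. None restores the automatic one at the thresholds. The Grade 4 stop that applies regardless of attribution (Section 10.5) covers Germany only.

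Two further points have some force. Case C concerns resumption rather than the NOTE, and a reader could reasonably let the specific liver restart rule override the general resume sentence; a cross-reference there is a minor clarification. The causality definitions in Section 10.3.4, where possibly related requires a temporal link "and the event is unlikely to be explained by" the medical condition or other therapies, point the same way as the NOTE. But the NOTE does not cite them and already demands exclusion of other causes, so they add little.

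**Conclusion.** The contradiction is real and should be fixed. For participants with normal baseline liver tests, one sentence makes the threshold stop mandatory, and a NOTE in the same subsection makes it conditional on an exercise that cannot be complete when the threshold is crossed. The conclusion rests on a literal reading of the NOTE and on the order of events set by the assessments subsection.

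The practical reach is small: at most 16 participants, about 12 on active drug, an unstated number of them with normal baselines, and monthly or quarterly dosing that lets many work-ups finish in time. The documents give no event rate and do not say how much dosing remained under this protocol version before the sponsor stopped the trial. The matter is one of participant safety and does not affect the reported results.

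**What to change.** Replace the NOTE with wording to this effect: study intervention is held as soon as any threshold above is met, whatever the suspected cause, and stays held during the work-up; causality and the exclusion of other causes are considered only when deciding on restart, under the restart rule in Assessments in Case of Increased Levels of Liver Blood Parameters.

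In Section 7.1.1, state that for item 2 the resume sentence is subject to that restart rule.

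This is a change of protocol wording only, with no new tests or visits. The cost is an occasional delayed or missed dose. It includes a prolonged hold when no alternative cause is definitively identified, because the restart rule then offers no route back to dosing.

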# Alternative DILI Monitoring Algorithm for Participants with Elevated Transaminases at Baseline

The following alternative DILI monitoring algorithm should be used in participants with elevated transaminases above ULN at baseline.

- **Close Monitoring**: If participants develop elevations of AST or ALT > 2 times the screening value or total bilirubin > 1.5 times the screening value while on the study, testing should be repeated within 48 to 72 hours. Persistent elevations should be followed by repeat testing and physical examinations 2 to 3 times per week with or without drug discontinuation.
- **Study Intervention Discontinuation**: Study intervention will be discontinued if a participant meets one of the following abnormal liver function conditions:
  - ALT or AST > 5 × the screening value in participants with a screening value  $< 2 \times ULN$

- ALT or AST > 3 × the screening value in participants with a screening value  $\geq$  2 × ULN but < 5 × ULN
- ALT or AST increase  $> 2 \times$  the screening value accompanied by a concomitant total bilirubin increase to  $> 2 \times$  the screening value OR an INR increase of > 0.2
- Elevations of liver enzymes accompanied by symptoms consistent with hepatic injury (e.g., fatigue, nausea, vomiting, right upper quadrant pain or tenderness, fever, rash, and/or eosinophilia [> 5%])

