### **Prior/Concomitant Therapy**

- 5. Use of an RNAi drug at any time.
- 6. History of one or more of the following reactions to an oligonucleotide-based therapy:
  - a. severe thrombocytopenia (platelet count < 100,000/ mm^3)
  - b. hepatotoxicity, defined as ALT or AST  $> 3 \times$  ULN and total bilirubin  $> 2 \times$  ULN or INR > 1.5
  - c. severe flu-like symptoms leading to discontinuation of therapy
  - d. localized skin reaction from the injection (graded severe) leading to discontinuation of therapy
  - e. coagulopathy/clinically significant prolongation of clotting time

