#### **Diagnostic assessments**

8. AST and  $ALT > 5 \times ULN$  at Screening

For individuals with any serum aminotransferase elevation  $> 2 \times ULN$ , autoimmune hepatitis should be ruled out through the appropriate screening tests, which may include total IgG or gamma-globulin levels and/or serologic markers (i.e., antinuclear antibodies, anti-smooth-muscle antibodies at a titer of at least 1:40, anti-liver/kidney microsomal-1 antibodies, anti-liver cytosol antibody [anti-LC 1], or antisoluble liver/liver pancreas [anti-SLA/LP] antibodies).

- 9. ALP  $2 \times$  ULN at Screening.
- 10. Serum AFP value > 100 ng/mL at Screening.

If AFP at screening is > ULN but < 100 ng/mL, the participant is still eligible if an appropriate hepatic imaging study reveals no lesions.

- 11. Positive screening for antimitochondrial antibodies (only required if primary biliary cholangitis is suspected).
- 12. Platelets < 100,000/mm^3 at Screening
- 13. INR  $> 1.6 \times$  ULN at Screening

14. Positive screening for HBsAg, HCV antibodies, or HIV1 and 2 antibodies. If a participant has been tested in the past 3 months, medical record documentation of this testing can be used for eligibility.

NOTE: In participants with previous treatment for hepatitis C with direct-acting HCV medication and seropositivity for HCV, or in participants with prior infection and spontaneous resolution, HCV RNA must be undetectable (at least 2 negative HCV RNA tests at least 12 weeks apart), and the HCV infection must have been resolved or cured > 3 years prior to enrollment.

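### The aminotransferase exclusion and the elevated-baseline DILI tiers do not meet at 5 × ULN, so some enrollable values have no enzyme-only stop

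*Protocol*

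**What the plan says.** Protocol Section 5.2, under Diagnostic assessments, excludes "AST and $ALT > 5 \times ULN$ at Screening". (It is item 8 there; a cardiovascular criterion earlier in the section also carries the number 8.) The note beneath it opens "For individuals with any serum aminotransferase elevation" and asks that autoimmune hepatitis be ruled out above 2 × ULN.

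Section 7.1.1.2 then splits participants by baseline:

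- The absolute limits (above 8 × ULN, or above 5 × ULN for more than two weeks) stand under the heading "For Participants with Normal Liver Biochemistries at Baseline".
- Anyone with transaminases above ULN at baseline follows the alternative algorithm, which has no upper limit on who enters it. Its two enzyme-only stops are more than 5 times the screening value when that value is below 2 × ULN, and "ALT or AST > 3 × the screening value in participants with a screening value" of at least "2 × ULN but < 5 × ULN".
- The other two stops in that algorithm need something besides the enzyme: a bilirubin or INR rise, or symptoms.

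Section 7.1.1 makes discontinuation mandatory when these liver criteria are met.

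**The concern.** The tiers end just below 5 × ULN, and the exclusion begins just above it and, as worded, needs both enzymes to be high. Elsewhere the protocol writes *or* when one enzyme is enough, for example "hepatotoxicity, defined as ALT or AST" in the prior-therapy exclusions and throughout the DILI criteria. A site reading *and* literally is therefore reading the text normally, and Section 8 allows no waivers.

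This is the first study of belcesiran in this liver disease, and Section 2.3.4 names raised liver tests among the key potential risks. The automatic transaminase-only stop would be missing for the highest baselines that can enrol, where a fixed numeric rule is most useful. The tiers also refer to a screening value without saying whether each enzyme is compared with its own, so two sites could handle the same participant differently.

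**Working it through.** The plan gives no figure to reproduce. The check is whether the enrollable screening range is fully covered by the enzyme-only tiers. All values are in × ULN, and *s* is the screening value of one enzyme.

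**Inputs**

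- Exclusion (Section 5.2): as written, excluded if AST > 5 and ALT > 5. The stricter reading is excluded if either is > 5.
- Lower tier (Section 7.1.1.2): if 1 < *s* < 2, stop above 5*s*.
- Upper tier (Section 7.1.1.2): if 2 ≤ *s* < 5, stop above 3*s*.
- Close monitoring (Section 7.1.1.2): above 2*s*. Stopping the drug is optional at this step.

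**Thresholds, enzyme by enzyme**

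| Screening value | Enzyme-only stop | Close monitoring |
|---|---|---|
| 1.5 | > 5 × 1.5 = 7.5 | > 3.0 |
| 2.0 | > 3 × 2.0 = 6.0 | > 4.0 |
| 4.0 | > 3 × 4.0 = 12.0 | > 8.0 |
| 4.99 | > 3 × 4.99 = 14.97 | > 9.98 |
| 5.0 | none | > 10.0 |
| 6.0 | none | > 12.0 |
| 8.0 | none | > 16.0 |

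**Exactly 5.0.** The value is not > 5, so it does not exclude. It is not < 5, so no tier applies. The result is the same whether the exclusion is read with *and* or with *or*.

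**One enzyme above 5, exclusion as written.** Take AST 4.0 and ALT 6.0. AST 4.0 > 5 is false, so the participant enrols. AST stops above 12.0. ALT 6.0 is not < 5, so it has no tier, and close monitoring of ALT starts only above 12.0.

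**Both enzymes at or above 5, exclusion as written.** Take AST 5.0 and ALT 6.0. AST 5.0 > 5 is false, so the participant enrols, and neither enzyme has an enzyme-only stop.

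**If the other enzyme selects the tier.** The text does not rule out letting AST place the participant in a tier that is then applied to ALT. For ALT 6.0 the stop would be above 3 × 6.0 = 18.0 when AST is 4.0, and above 5 × 6.0 = 30.0 when AST is 1.5. So the ALT stop could be none, 18 or 30 depending on interpretation. This reading gives no rescue when both enzymes are at or above 5.

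**Stricter reading of the exclusion.** If either enzyme above 5 excludes, the uncovered set shrinks to the single value 5.0.

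**The case against.** The strongest reply is that *and* was meant as a list, with each enzyme having its own limit of 5 × ULN. The protocol does use *and* loosely. Section 7.1.1.1 speaks of events A and B and shortly afterwards of A or B. Section 4.1 has participants randomized to either Cohort 1 and 2. The viral serology exclusion names HIV1 and 2 antibodies, which cannot sensibly require both. An upper tier that ends at 5 × ULN also suggests the authors thought nobody above that level could enrol. On this reading the gap is one boundary value, and there is no evidence that any participant sits there.

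The reply adds that the 18 and 30 × ULN figures rest on an unnatural reading, that each enzyme below 5 × ULN keeps its own stop, and that other protections remain. These are the bilirubin/INR and symptom criteria, close monitoring, the instruction "If close monitoring is not possible the trial product should be discontinued", the individual stopping rule "Safety concerns as judged by the Investigator", and the general exclusion for any condition the investigator thinks might endanger the participant.

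Much of this stands. The intended exclusion may well have been per enzyme, the 18 and 30 × ULN figures are conditional, and participants are not left without liver protection. It does not remove the defect. Exactly 5.0 × ULN is uncovered on either reading, the eligibility rule as written admits a single higher enzyme, and none of the remaining safeguards is a numeric stop on the transaminase alone.

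**Conclusion.** The point holds. At exactly 5.0 × ULN there is no enzyme-only discontinuation threshold under any reading. As the exclusion is written, the same is true of a single enzyme at any level above 5 × ULN, provided the other is not above 5 × ULN. The wider gap rests on the literal *and*; the boundary gap does not.

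What is missing is one automatic stop, not liver monitoring as a whole. The documents do not say how many participants, if any, had such values. Section 1 of the SAP records that the sponsor stopped the trial before Cohort 3 enrolled, so the practical effect now is limited. It is still a mandatory safety rule that is wrong as written, and worth correcting wherever the wording is used again.

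**What to change.** - **Section 5.2:** exclude AST *or* ALT above 5 × ULN at Screening.
- **Section 7.1.1.2:** let the upper tier run from 2 × ULN up to and including 5 × ULN. Equivalently, exclude either enzyme at or above 5 × ULN and leave the tier as it is.
- **Section 7.1.1.2:** state that each enzyme is judged against its own screening value.

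With the first two changes, a screening value of 5.0 × ULN stops above 3 × 5.0 = 15 × ULN, and ALT 6.0 × ULN is excluded. Changing only *and* to *or* would leave 5.0 × ULN open.

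A changed exclusion does nothing for people already enrolled, so the sponsor should check recorded screening ALT and AST in Cohorts 1 and 2 for values at or above 5 × ULN.

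The cost is a few words in two sections, with no new data and no SAP change. In a running trial it would go through a protocol amendment with ethics approval (Section 10.1.1).
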